The initial treatment of Patients with Functional constipation is based on fiber. There are multiple fiber products in the market, which are Promoted as a supplement for constipation without any scientific evidence to support ITS use. Furthermore, the tolerability of These compounds limits long-term Their use in esta patient population. Scientific evidence is required to support the effectiveness in the use of These fiber supplements in Patients With functional constipation.

6. Justification

There are multiple fibers are in the market That Promoted as a beneficial supplement for Patients With constipation, DESPITE esta, there is not enough scientific evidence derived from randomized and controlled studies to support ITS use. THEREFORE, it is Necessary to Provide evidence to support the use of blue agave fructans Tequilana Weber in Patients With functional constipation.

7A. hypothesis

Defined as a verifiable statement About the relationship Between a variable-dependent and an independent variable. (Remember That the concepts of "null hypothesis", "alternate hypothesis" are related to the statistical analysis So They Should not be included in this item)

General Hypothesis:

Plantago Psyllium When Compared With, the blue agave fructans Weber Tequilana have a like effect or are more effective in Improving functional constipation in adult patients.

Objectives

PRIMARY

1. To Evaluate the efficacy of the blue agave fructans Tequilana Weber in Patients With functional constipation.

SECONDARY

1. To compare the efficacy and tolerability of 5 and 10g doses of blue agave fructans Tequilana Weber in Patients With functional constipation.
2. To Evaluate the impact of the consumption of blue agave fructans Tequilana Weber on the quality of life of the subjects WHO ingest it by Applying the quality of life questionnaire SF-36.
3. To determine the impact of the blue agave fructans of Weber Tequilana intake in the fasting glucose, glycosylated hemoglobin A1c and the lipid profile (metabolic profile) of the subjects WHO ingest it.
4. To Evaluate the presence of short chain fatty acids (butyrate) before vs after the treatment with blue agave fructans Tequilana Weber.
5. To determine the impact of the ingestion of blue agave fructans Tequilana Weber in the microbiota before vs after ingestion.
6. Evaluate to the tolerance to the ingestion of blue agave fructans Weber Tequilana through the use of breath test.

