spontaneous evacuation It is defined as an evacuation in the absence of use of laxatives, suppositories or enemas and complete evacuation is defined as spontaneous evacuation to that sensation of incomplete emptying of the rectal ampulla.

secondary measured variables:

- I. Effect of supplementation of fructan Weber blue agave Tequilana in the form of bowel movements, assessed by the Bristol scale. It is defined as a change in the form of evacuations when presenting a change in the classification of Bristol, more than 50% according to the daily evacuations taking the average of the evacuations submitted within 15 days.

- II. Effect of supplementation of fructan Weber blue agave Tequilana in the frequency of bowel movements. It shall be defined as responder presenting increased 50% in stool frequency compared with baseline, according to the daily bowel movements taking the average of evacuations presented at 15 days.
- III. Evaluate the impact of the concentration of short-chain fatty acid, particularly butyrate, in the feces of subjects before and after addition of fructans Tequilana Weber blue agave. The butyrate concentration was determined by method of gas chromatography and the increase will be assessed in millimoles per liter.
- IV. Evaluate the impact of supplementation fructans Weber blue agave Tequilana the microbiota by determining edges present in feces of the subjects before and after the supplementation fructan derivatives fiber; which are:
 - 1) **Actinobacterias** (Bifidobacteriales)
 - 2) **Bacteroidetes** (Prevotella, Paraprevotela, Ruminococcaeaceae, Faecalibacterium)
 - 3) **Firmicutes** (Veillonella, Anaerostipes, lactobacilli Clostridiales, Enterococcus)
 - 4) **Proteobacteria** (Bilophila, Escherichia).
 - 5) **Euryarchaeota** (Methanobacteriales)
- V. To evaluate the impact of serum glucose concentration and HbA1c fasting serum of subjects before and after addition of fructans Tequilana Weber blue agave. HbA1c concentration is determined as it is intended to monitor the impact of fiber on glucose throughout the duration of the study (2 months) and in order to avoid the variability that fasting glucose.

Gas Chromatography: (determination of short-chain fatty acid AGCC)

AGCC for determining ion detector flame will be used. The following steps are performed:

1. ethylbutyrate - 1 g of faeces which is added 50 uL of 2 homogenizará.
2. 1 mL of hydrochloric acid was be added.

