Sequencing and analysis of the amplified fragments is by fluorescent sequencing equipment terminator 3130 / genetic analyzer (Applied Biosystems).

The PCR products were sequenced and analyzed and will be submitted to GenBank for species identification.

Extracting bacterial DNA and quantitation of bacterial species used to demonstrate the prebiotic effect of agave fiber, since selective growth of the population of bifidobacteria and lactobacilli and occurrence of short-chain fatty acid in stool is expected.

Thus in addition to the functional properties and their effects on constipation, you may check the prebiotic effect of agave fructans.

Data analysis:

a) Statistical analysis plan

The data obtained will be analyzed with SPSS version 24. For continuous variables the results are presented in mean ± standard deviation when the variables are normally distributed or medians and percentiles otherwise and as frequency and percentages when they were categorical. For basal and subsequent comparison to the intra intervention groups, Student's t-test for paired samples (variables with normal distribution) or the Mann-Whitney U (variables without normal distribution) is used in the case of continuous variables and X² or the McNemar test in the case of categorical variables. For comparison between groups ANOVA (variables with normal distribution) or Kruskal-Wallis (non-normal distribution variables) used for continuous variables and the same percentage of change obtained when the variables are continuous.

Also an analysis of covariance (ANCOVA) was performed to control variables that might have an effect on the response variables.

b) Non-inferiority study

There are multiple fibers on the market that are promoted as beneficial supplement to patients with constipation; Despite this, there is insufficient scientific evidence from randomized controlled trials to support its use. Psyllium psyllium, is the first-line treatment used for such functional bowel disorder; fructans tequilana Weber blue variety are soluble fibers which are rich fructooligosacáridos role in prebiotic substance with the which is associated with a number of health benefits including intestinal health; therefore, as an alternative treatment in patients with constipation using these fructans it is raised to generate clinical evidence and demonstrate the therapeutic potential similar to plantago psyllium.

c) Sample size

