The sample size was calculated from the formula mean differences for non-inferiority studies and data from 52 studies were used Holscher HD., Et a38, Erdogan A., et al 53 and R Closa-Monasterolo , et al 54. accuracy of 95% (0.05 probability of making an error or type I was used α) And a force or power of 80% (0.20 probability of committing a type II error or β).

$$n = \lambda/\Delta.$$

Where:

n = sample size

$$\lambda = 10.91$$

$$\Delta = 1$$

Where:

$$\Delta = \frac{1}{(\sqrt{\sum \sigma^2})} (\sum \sigma)$$

$$\sigma_1 = 0.01$$

$$\sigma_2 = 0.12$$

$$\sigma_3 = 0.43$$

$$\sigma_4 = 0.27$$

$$= \Delta \frac{1}{(0.82)} (0.82) = 1$$

$$= 10.91 \approx 11 n = 10.91/1$$

Taking a 20% loss during the study sample size are:

$$n = 13 \approx 15$$

d) Statistical significance

It is considered each of the variables under study as the statistically significant with a value of $p < 0.05$

e) Statistical analysis of the population

The study population are volunteers with functional constipation and statistically analyzed considering the per protocol population and intent-to treat.

f) statistical treatment

It does not, in our strategy of statistical analysis a power of 80% for our study with an alpha of 0.05 is contemplated to demonstrate non-inferiority. Therefore, a greater percentage of losses accepted 20% to give validity to our study.

11. List of materials to use resources.

Team	Model	Description
portable stadiometer	Seca213	Measuring range 20-205 cm Division 1 mm Brand: Seca
Impedance	RJLQIV	Impedance Analyzer Brand: RJL Systems Includes: analyzer, charger case, LEMO cables, resistor, 400 electrodes, software
Weighing machine	BBZ-420	Maximum capacity up to 140 Kg minimum division 100 g Zamac bar with matt chrome Pylons cursors zamac beige or white enameled Base 54 x 20 x 10.5 cm Scale weight: 17 kg authorization NOM Made from sheet metal Finished in baked enamel paint

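### Within-arm before/after comparisons of non-normal variables are assigned the Mann-Whitney U, an independent-samples test, although the same patients are measured twice

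*Combined protocol and SAP*

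**What the plan says.** The tests are listed under Data analysis, a) Statistical analysis plan. One sentence covers comparisons over time within an arm, opening with "For basal and subsequent comparison to the intra intervention groups". For continuous variables it specifies that the "t-test for paired samples (variables with normal distribution) or the Mann-Whitney U (variables without normal distribution) is used". For categorical variables it offers "X² or the McNemar test in the case of categorical variables".

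The next sentence deals with the arms against each other: "For comparison between groups ANOVA (variables with normal distribution) or Kruskal-Wallis (non-normal distribution variables) used for continuous variables". It names no categorical test.

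Several secondary outcomes are before/after measurements on the same people. Secondary objective 5 looks for an effect "in the microbiota before vs after ingestion", and secondary objective 7 does the same for gastrointestinal transit. Secondary variable III measures butyrate "in the feces of subjects before and after addition of fructans Tequilana Weber blue agave", and variable V treats fasting glucose and HbA1c in the same way.

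**The concern.** Whether two sets of values are paired depends on the design, not on the shape of their distribution. Here one sentence treats the data as paired when they are normal (paired t-test) and as unpaired when they are not (Mann-Whitney U). An analyst who follows the plan to the letter would discard the link between a patient's first and second value just where the variable is skewed.

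At stake is the ability to detect within-arm change in small arms: 15 patients are planned per arm. The outcomes exposed are continuous, before/after and judged non-normal, for example bacterial counts or transit. Butyrate is a less certain example, because variable III also says that the increase will be assessed, which could mean an analysis of differences.

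Two smaller gaps sit in the same sentences. The plan does not say when X² and when McNemar applies; used on the same patients at two visits, X² would have the same fault. It also does not say whether normality is judged on each visit's raw values or on the paired differences. The differences are what matter for the paired t-test.

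**Working it through.** **Reading the text.** The within-arm sentence and the between-arm sentence are separate. The between-arm sentence already has its rank test (Kruskal-Wallis). The Mann-Whitney U appears only in the within-arm sentence, and no section names a signed-rank or other paired rank test. There is no stated figure to reproduce, because the plan gives no calculation for these comparisons.

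**Inputs from the documents.** 15 patients per arm (paragraph on patients to include); significance at p < 0.05 (Data analysis, d), sidedness not stated, two-sided used here; a 20% loss (c) Sample size), which leaves 15 × 0.80 = 12 per arm.

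**Inputs assumed.** The within-patient correlation r, the distribution (lognormal, log-SD 0.6) and the shift. The documents give none of these.

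**Why the error rate moves.** The Mann-Whitney reference distribution assumes independent samples. As a rough guide, a difference between two visits has variance proportional to 2(1 − r), while the test assumes 2. The true two-sided error is then about 2Φ(−1.96/√(1 − r)):

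- r = 0.3: 1.96/√0.7 = 2.34, giving about 1.9%
- r = 0.5: 1.96/√0.5 = 2.77, giving about 0.6%
- r = 0.7: 1.96/√0.3 = 3.58, giving about 0.03%
- r = −0.3: 1.96/√1.3 = 1.72, giving about 8.6%

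**Simulation.** 20,000 runs per cell, exact two-sided 0.05 tests, n = 15. The shift is in SD units on the log scale. Each cell shows Mann-Whitney / signed-rank rejection.

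| r | No shift | 0.6 SD | 0.8 SD |
|---|---|---|---|
| 0 | 4.5% / 5.1% | 32% / 30% | 52% / 49% |
| 0.1 | 3.5% / 4.7% | 31% / 32% | 53% / 53% |
| 0.3 | 1.8% / 4.7% | 31% / 41% | 53% / 62% |
| 0.5 | 0.9% / 4.8% | 28% / 52% | 54% / 77% |
| 0.7 | 0.2% / 4.9% | 25% / 73% | 56% / 93% |

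Relative loss of power is 1 − (Mann-Whitney ÷ signed-rank). At r = 0.5 it is 1 − 0.280/0.519 = 46% for 0.6 SD and 1 − 0.539/0.765 = 30% for 0.8 SD. At r = 0.3 it is 25% and 15%; at r = 0.7 it is 66% and 40%.

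With 12 patients per arm the relative loss is nil for r up to 0.1, 15–24% at 0.3, 34–49% at 0.5 and 50–70% at 0.7.

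**Separate check.** A second simulation (10,000 runs, n = 15, shift 0.7 SD on the log scale) gives Mann-Whitney power of 0.40 at r = 0.5 and at r = 0.7, against 0.62 and 0.82 for the signed-rank test. At r = −0.3 the Mann-Whitney error rises to about 8%.

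**Sensitivity to the scale of the shift.** With an additive shift of 0.6 raw SD on the same lognormal data, power is 55% vs 56% at r = 0.3, 58% vs 70% at r = 0.5 and 57% vs 84% at r = 0.7. The relative losses are 1 − 55/56 ≈ 2%, 1 − 58/70 ≈ 17% and 1 − 57/84 ≈ 32%.

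**How often the branch is used.** This depends on the unstated normality rule. If Shapiro-Wilk were the rule (an assumption), then at n = 15 and a 0.6 SD shift it would reject for at least one visit's raw values in 70–77% of samples (r from 0.1 to 0.7), but for the paired differences in only 24–34%.

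**The case against.** **Intent.** The text reads as a translation and may have merged two lists. Secondary objective 1 compares the 5 g and 10 g doses, a two-arm contrast that the Mann-Whitney U would suit and for which no two-group test is named. The name could be misplaced, not wrongly chosen. That is fair, but it does not rescue the plan: if the test belongs elsewhere, the within-arm non-normal case has no test at all.

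**Size.** Distribution, shift and correlation are all assumed, and the loss shrinks on an additive scale. This stands, and the size should be read as anything from none to large. The distortion of the type I error does not depend on the scale of the shift, because it is computed with no shift.

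**Frequency of use.** If normality is judged on the differences, the branch is reached in a minority of samples, and the power figures are averages over all samples, not only those. This also stands. But the plan does not state that rule, and under the raw-value reading the branch is reached in most samples.

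**Importance.** These are uncontrolled within-arm secondary comparisons. The plan also has between-group tests, including on percentage change, and an ANCOVA. This is correct, and it limits the weight of the point. The before/after objectives are nevertheless stated ones.

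**Conclusion.** The point holds. As written, the plan applies an independent-samples test to paired data for non-normal within-arm comparisons, and nothing else in the documents corrects it. This is a wrong test name, not a missing detail.

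Under positive within-patient correlation the consequence is missed changes, not false positives. Only a negative correlation would inflate the error rate. The size rests on assumed correlation, distribution and scale of shift: no loss near r = 0, and a relative power loss at n = 15 of about 30–46% at r = 0.5 for log-scale shifts, or about 17% for an additive shift of 0.6 raw SD.

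The between-arm comparisons, the non-inferiority question and outcomes already defined as change or response from baseline are not affected. It should be corrected, but it does not threaten the main conclusion of the trial.

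**What to change.** In Data analysis, a) Statistical analysis plan:

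- For within-arm continuous comparisons, replace the Mann-Whitney U with the Wilcoxon signed-rank test, and state that normality is judged on the paired differences.
- Keep Kruskal-Wallis for the four-arm comparison. If a two-arm rank test is wanted for 5 g against 10 g, name it in the between-group sentence.

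While that text is open, three clarifications are worth adding:

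- Move X² to the between-group sentence. Use McNemar for paired binary outcomes, and a marginal-homogeneity test only if an outcome such as Bristol form is analysed with more than two categories.
- Name the pair of visits tested for each outcome. Blood is drawn at visits 3, 4 and 5, and stool is collected at those visits and at the final one.
- Say whether butyrate is analysed as two values or as the increase.

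The core correction takes one or two sentences. No new data, visits or patients are needed.

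### The plan sets a non-inferiority aim against psyllium but lists only tests of difference, with no identifiable margin, confidence-interval rule or agave-minus-psyllium contrast

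*Combined protocol and SAP*

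**What the plan says.** **Aim.** The general hypothesis (section 7A) is that agave fructans work about as well as psyllium, or better. Data analysis b), headed as a non-inferiority study, wants to "demonstrate the therapeutic potential similar to plantago psyllium". Data analysis c) sizes the trial from the "formula mean differences for non-inferiority studies". Data analysis f) also links power to non-inferiority, but the sentence is garbled: "It does not, in our strategy of statistical analysis a power of 80% for our study with an alpha of 0.05 is contemplated". The point does not need it.

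**Method.** Data analysis a) states: "For comparison between groups ANOVA (variables with normal distribution) or Kruskal-Wallis (non-normal distribution variables) used for continuous variables". It adds: "Also an analysis of covariance (ANCOVA) was performed to control variables that might have an effect on the response variables". No covariates and no contrast are named. Data analysis d) treats "each of the variables under study as the statistically significant with a value of" p below 0.05. Data analysis e) plans the "per protocol population and intent-to treat" sets.

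**Objective, arms and endpoint.** The primary objective, and the design statement in section 8, concern the efficacy of agave and do not mention psyllium. There are 60 patients in four arms of 15: three agave, one psyllium. The main outcome (section 10) is a rise of at least one complete spontaneous evacuation from baseline. Its timepoint is not given, nor whether it is analysed as a count or as a responder rate.

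**The concern.** A test of difference asks whether the arms are distinguishable. Non-inferiority asks whether agave could be worse than psyllium by more than a tolerable amount, and that needs the amount, a named comparison and an interval rule. Without them the listed tests can support only the second half of the hypothesis (agave better), and only after an agave-versus-psyllium contrast is added. They cannot support the first half.

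The trial's central comparative claim is at stake. If agave is not significantly better, the temptation will be to read p>0.05 as similarity. For a given true deficit, that result becomes more likely as the arms get smaller. A margin chosen after the results are seen could be fitted to them.

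**Working it through.** **1. The plan's own sample size.** From Data analysis c): λ = 10.91, Δ = 1, so n = λ/Δ = 10.91/1 = 10.91, rounded to 11. For the loss ("Taking a 20% loss during the study sample size are"), 10.91 × 1.2 = 13.1, printed as 13 and rounded to 15. The step from λ and Δ to n reproduces.

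**2. Is a margin among the inputs?** Two figures could be mistaken for one.
- Δ = 1 is printed as 0.82/0.82, both terms built from the four sigmas (0.01, 0.12, 0.43, 0.27). As printed it is a ratio of sigmas, not a tolerable deficit on an outcome scale.
- The one-evacuation rise in section 10 is a change within a patient from baseline, not a difference between arms.

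**3. How often would the ANOVA miss a real deficit?** The documents give neither a margin nor an outcome SD, so the deficits d are assumptions in SD units. The endpoint is assumed continuous and approximately normal.

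With psyllium at 0 and the three agave arms at −d, the mean is −0.75d. The squared deviations sum to 3(0.25d)² + (0.75d)² = 0.75d², so the noncentrality is n × 0.75d². The degrees of freedom are 3 and 4n − 4, with alpha 0.05. Twelve per arm is 15 × 0.8.

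| n per arm | d (SD) | noncentrality | P(non-significant) |
|---|---|---|---|
| 15 | 0.5 | 2.81 | 76% |
| 15 | 0.75 | 6.33 | 49% |
| 12 | 0.5 | 2.25 | 80% |
| 12 | 0.75 | 5.06 | 59% |

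**4. Width of one pairwise comparison.** The 95% half-width in SD units is t(0.975, 2n − 2) × √(2/n).
- n = 15: 2.048 × 0.365 = 0.75 SD.
- n = 12: 2.074 × 0.408 = 0.85 SD.

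An observed difference of zero at 15 per arm would therefore still leave a deficit of up to about 0.75 SD inside the interval.

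**5. Margin that 15 per arm could support.** Setting noncentral-t power to 80% with no true difference and no baseline adjustment:

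| One-sided alpha | Two-arm error (28 df) | Pooled four-arm error (56 df) |
|---|---|---|
| 0.025 | 1.06 SD | 1.04 SD |
| 0.05 | 0.93 SD | 0.92 SD |

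Adjustment for baseline would lower these by an amount that the documents do not allow one to calculate.

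**The case against.** Several objections have force.

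- **More than p-values will be reported.** Data analysis a) plans means with SDs or medians with percentiles, frequencies and percentages, and percentage change. A reader might infer that a non-significant p would be the only output; that is not so. What is missing is a rule that turns those summaries into a non-inferiority conclusion.
- **The text is damaged.** The translated sentence on within-group comparisons also lists Mann-Whitney and chi-square, which normally compare independent groups, so the split between within-group and between-group methods is uncertain. These are tests of difference too. The Δ formula may also be corrupted. It is therefore safer to say that no margin can be identified than that the sponsor never had one.
- **The endpoint may be binary.** Section 10 can be read as a responder definition. The SD-based figures would then not apply directly. The missing rule would be the same.
- **ANCOVA could supply the contrast, and both analysis sets are planned.** Both are useful and the fix relies on them, but neither replaces a margin and an interval.
- **Superiority is part of the hypothesis.** A significant advantage over psyllium would also support non-inferiority. The gap concerns every other result.

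Two stronger readings are tempting. One is that 15 per arm is too few for non-inferiority; the documents do not support this, because adequacy depends on a margin that is not stated. The other is that the sponsor intends to read non-significance as similarity; nothing in the plan says so.

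**Conclusion.** Wrong as written, and it must be fixed. The hypothesis and Data analysis b) and c) set a similarity or non-inferiority aim against psyllium, while Data analysis a) and d) provide only tests of difference at p<0.05. This is a mismatch between claim and method, not just missing detail, because the listed tests cannot show a like effect at any sample size.

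The missing rule holds whatever the endpoint scale. The error rates and interval widths rest on a continuous, roughly normal endpoint, and the error rates also on assumed deficits. On those terms, true deficits of 0.5 to 0.75 SD in all agave arms would escape the ANOVA in about half to three quarters of trials at 15 per arm, and in 59% to 80% at 12.

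**What to change.** 1. State the primary endpoint's scale and timepoint, and align the primary objective with the psyllium comparison.
2. If non-inferiority is kept, estimate agave minus psyllium for the named agave arm or arms, in a stated order or with multiplicity control. Use the planned ANCOVA adjusted for baseline if the endpoint is continuous, or a difference in proportions if it is binary.
3. State one alpha and its matching interval: one-sided 0.025 with a two-sided 95% interval, or one-sided 0.05 with a two-sided 90% interval. With M the pre-stated, sponsor-justified margin (a positive number) and higher values better, claim non-inferiority only if the lower limit is above **minus** M. Report this in both the intention-to-treat and per-protocol sets, and say how the two are used together.
4. State that a non-significant ANOVA, Kruskal-Wallis or ANCOVA result is not evidence of similarity.
5. If no justifiable margin is achievable at 15 per arm, drop the non-inferiority claim and its 80% power statement, and report differences with confidence intervals.

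**Cost.** These are text changes that need no new visits or data, but the sponsor must choose and defend a margin. The downside is that the result may be inconclusive: for a continuous endpoint, unadjusted, only margins of roughly 0.92 to 1.06 SD or wider (depending on alpha and error df) reach 80% power at 15 per arm. Baseline adjustment would lower that threshold.
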